# APPENDIX 2. OUTCOME MEASURE TOOLS AND ASSESSMENTS

This appendix contains:

- The VEINES Quality of Life questionnaire (from Lamping et al, 2003)
- Visual analogue pain scale and the visual analogue pruritis scale (Jonker et al, 2020)
- EQ-5D-5L quality of life score (from Herdman et al, 2011)

#### **VEINES QoL questionnaire**

#### INSTRUCTIONS HOW TO ANSWER:

Answer every question by marking the answer as indicated. If you are unsure about how to answer a question, please give the best answer you can.

Below are some questions about your views about your legs. This information will help keep track of how you feel and how well you are able to do your usual activities.

1.	During the past 4 weeks, how often have you had any of the following leg problems?					
	(check one box on each line)	Every day	Several times a week	About once a week	Less than once a week	Never
1.	Heavy legs	1	2	3	4	5
2.	Aching legs	1	2	3	4	5
3.	Swelling	1	2	3	4	5
4.	Night cramps	1	2	3	- 4	5
5.	Heat or burning sensation	1	2	3	4	5
6.	Restless legs	1	2	3	4	5
7.	Throbbing	1	2	3	4	5
8.	Itching	1	2	3	4	5
9.	Tingling sensation (e.g.pins and needles)	1	2	3	4	5

2.	At what time of day is your leg problem	most intense ? (check one)
	1 On waking	4 During the night
	2 At mid-day	5 At any time of day
	3 At the end of the day	6 Never

#### 3. Compared to one year ago, how would you rate your leg problem in general now? (check one)

- 1 Much better now than one year ago
- Somewhat worse now than one year ago 4
- 2 Somewhat better now than one year ago
- 3 About the same now as one year ago
- Much worse now than one year ago 5
- I did not have any leg problem last year 6
- 4. The following items are about activities that you might do in a typical day. Does your leg problem now limit you in these activities? If so, how much ?

	(Check one box on each line)	l do not work	YES, Limited A Lot	YES, Limited A Little	NO, Not Limited At All
a.	Daily activities at work	0	1	2	3
b.	Daily activities at home (e.g. housework, ironing, doing jobs/repairs around the house, gardening, etc)	odd	1	2	3
C.	
 
Social or leisure activities in which you are standing for long periods (e.g. parties, weddings, taking public transportation, shopping, etc)
 
		1	2	3
d.	Social or leisure activities in which you are sitting for lor (e.g. going to the cinema or the theater, travelling, etc	ng periods )	1	2	3

5. During the past 4 weeks, have you had any of the following problems with your work or other regular daily activities as a result of your leg problem?

	(check one box on each line)	YES	NO
a.	Cut down the amount of time you spent on work or other activities	1	2
b.	Accomplished less than you would like	1	2
C.	Were limited in the kind of work or other activities	1	2
d.	Had difficulty performing the work or other activities (for example, it took extra effort)	1	2

During the past 4 weeks, to what extent has your leg problem interfered with your normal social activities with 6. family, friends, neighbors or groups? (check one)

1 Not at all	4	Quite a bit
2 Slightly	5	Extremely
3 Moderately		

7. How much leg pain have you had during the past 4 weeks? (check one)

None

4 Moderate

2 Very mild

5 Severe

3 Mild

- 6 Very severe
- 8. These questions are about how you feel and how things have been with you during the past 4 weeks as a result of your leg problem. For each question, please give the one answer that comes closest to the way you have been feeling. How much of the time during the past 4 weeks -

	(check one box on each line)	All of the Time	Most of the Time	A Good Bit of the Time	Some of the Time	A Little of the Time	None of the Time
a.	Have you felt concerned about the appearance of your leg(s) ?	1	2	3	4	5	6
b.	Have you felt irritable ?	1	2	3	4	5	6
C.	Have you felt a burden to your family or friends?	1	2	3	4	5	6
d.	Have you been worried about bumping into things ?	1	2	3	4	5	6
e.	Has the appearance of your leg(s) influenced your choice of clothing ?	1	2	3	4	5	6

# Visual analogue pain

# Pain visual analogue scale Instructions:

"Please think about any **leg pain** you may have had over the past **2 weeks** and put a cross along the scale that best describes it."

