#### Sample and recruitment

#### a) Patient recruitment

40 patients will be recruited for having bilateral leg ulceration and being treated in compression bandages or being in compression bandages for the prevention of leg ulceration (re-)occurrence.

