# Compression bandage selection procedure

The choice to apply 'full compression' versus 'reduced compression' will be dictated by the aetiology of the ulcer, wound assessment etc as per standard care. However, one leg will be bandaged in 'paste' compression and one leg in 'dry' compression, through a process of randomisation, using pre-prepared sealed envelopes.

The two types of compression bandages that will be used in this study are 'standard care' and are:

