# Timeline

Each patient participant will be consented at time of recruitment. A patient information sheet will be offered. Each leg will be randomised to either  $S_1F/S_1R$ ,  $S_2F/S_2R$  or  $S_3F/S_3R$ . The Research Nurse will visit each patient participant where they receive their treatment at Week 0, Week 1, Week 4, and Week 8. All participants will have demographic data obtained and the following outcome measures (Table 1):

Weeks	0	1	4	8
Baseline measures (demographics, medical history, vascular history; nursing teams and setting)	~			
Visual analogue pain score (pre, during and after dressing change)	~	~	~	~
Visual analogue pruritus score	~	~	~	~
EQ-5D-5L	~			~
VEINES-QoL	~			~
Patient and Nurses Experience		
 
✓
 
	~	~
questionnaire				
Nurses technical questionnaire		✓	~	~
Photo(s) of both legs	~	✓	✓	✓

Table 1. Outcome measures

- a) Baseline measures (see Appendix 1)
- b) Visual analogue pain score (see Appendix 2)
- c) Visual analogue pruritus score (see Appendix 2)

- d) VEINES-QoL is a patient reported outcome measure score that focuses on lower limb health (see Appendix 2)
- e) EQ-5D-5L is a general quality of life measurement tool (see Appendix 2)
- f) Patient questionnaire for comfort at application, during wear and on removal, fluid handling (see Appendix 3).

During the recruitment process the research team will acts as a contact point and coordinator for patients requiring information and support. If concerns are raised on participants (mental) wellbeing based on the home visits or outcome of the assessments, referral of patients/families on to other professional agencies will be done as appropriate and according to the Trust guideline.

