# Safety

There is no anticipated personal safety risk associated with taking part in this study. Appropriate precautions are in place to ensure medical and personal information is kept safe through adhering to appropriate governance regulations.

Participants will be allocated compression bandages that are used for its intended licensed purpose, are considered standard care in the Trust and that are available via NHS procurement routes.

Apart from being allocated to a different type of compression bandage per leg, all patients will be commenced on a compression therapy; therefore, all patients will receive the indicated clinical care they would receive if they were not in the study; they will be cared for in exactly the same manner as they normally would bar that usually both legs would be compressed using the same product for ease of procurement. However, in standard care, it is not unusual to be prescribed two different brands of compression bandages. Some bandage types may be more comfortable at controlling symptoms such as pruritus.

Participants cannot claim payments, reimbursement of expenses or any other benefits or incentives for taking part in this research.

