# Pruritus visual analogue scores Pruritus visual analogue scale Instructions:

"Please think about any **leg itching** you may have had over the past **2 weeks** and put a cross along the scale that best describes it."

Not itchy at all

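### The pain and pruritus VAS take one score for both legs although each leg wears a different bandage type, so neither scale can be attributed to paste or dry

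*Protocol*

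**What the plan says.** The allocation is within the patient. Under Compression bandage selection procedure, "one leg will be bandaged in 'paste' compression and one leg in 'dry' compression, through a process of randomisation". The Safety section agrees: "Apart from being allocated to a different type of compression bandage per leg, all patients will be commenced on a compression therapy". The planned sample is 40 patients, hence 80 legs.

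Table 1 (Timeline) lists the pain VAS and the pruritus VAS as outcome measures at Weeks 0, 1, 4 and 8. It asks for pain before, during and after the dressing change. It does not say that either scale is taken per leg.

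Appendix 2 gives the instructions to the patient. For pain: "Please think about any leg pain you may have had over the past 2 weeks". For itch: "Please think about any leg itching you may have had over the past 2 weeks". Each asks for one cross on one scale.

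Appendix 3 is built differently. Its patient and nurse questionnaires are printed once for the right leg and once for the left, each with the bandage code. They are scheduled at Weeks 1, 4 and 8, not at Week 0.

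**The concern.** The leg is the randomised unit, but the two dedicated symptom scales are answered by the patient as a whole. A patient whose paste leg is calm while the dry leg itches, and a patient in the mirror-image situation, can mark the same point on the line.

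This matters because the Safety section suggests that bandage types may differ in controlling symptoms such as pruritus, and the Data analysis section expects guidance on bandage selection to follow. As worded, the itch scale cannot inform that question. A change from Week 0 to Week 8 would be an uncontrolled before-after change in people wearing both products, and could be misread as an effect of one of them. The leg label must be captured when the form is completed, so this cannot be left to an analysis plan.

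**Working it through.** The protocol states no power, effect size or standard deviation for these scales, so there is no figure to reproduce. The check is whether a paste-minus-dry difference can be estimated at all.

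**1. One score per patient.** Write the score of patient i as y_i = m + P·p_i + D·d_i + error, where p_i and d_i mark whether the patient wears paste and dry.
- By the allocation rule, p_i = d_i = 1 for all 40 patients.
- The three columns of the design matrix are identical, so its rank is 1. Only the sum m + P + D can be estimated. P − D cannot, whatever the sample size.
- This does not depend on the additive form. However a patient merges two legs into one cross, every patient has the same exposure, so there is nothing to contrast.

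**2. By product.** Every patient has S3 (paste) on one leg and S1 or S2 (dry) on the other. A patient-level score then allows only S1 versus S2, a dry-versus-dry comparison between patients. S3 against the mean of S1 and S2 is not estimable.

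**3. One score per leg.** With y for each leg, the difference d_i = y_i(paste) − y_i(dry) removes the patient effect, and its mean estimates the paste-dry difference.

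**4. Which visits would give a usable difference.** Assume the allocated bandages go on at Week 0 and the two-week recall is kept.

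| Visit | Recall window (weeks) | Use |
|---|---|---|
| 0 | −2 to 0 | per-leg baseline |
| 1 | −1 to 1 | mixed: half the window precedes allocation |
| 4 | 2 to 4 | after allocation |
| 8 | 6 to 8 | after allocation |

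This gives up to 40 differences at each of Weeks 4 and 8, and at Week 1 only with a shorter recall.

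**5. Scale of what becomes visible.** Assume two-sided alpha 0.05 and 80% power (neither is in the protocol). The detectable mean difference, in standard deviations of the paired differences, is (1.96 + 0.84)/√n:
- n = 40 pairs: 0.44
- n = 36 pairs: 0.47
- n = 32 pairs: 0.50

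These figures only give a sense of size. The study plans descriptive analysis, not a test.

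**6. Recording burden.** Three pain readings plus one itch reading make 4 lines per visit. Split by leg, that is 8, so 4 extra.

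**The case against.** The strongest reply is that this is a realist evaluation with descriptive and thematic analysis, no confirmatory comparison, and a stated premise that the systems work equally well. Leg-level evidence also exists already. Appendix 3 asks, by leg and bandage code, about pain, comfort, skin condition and skin irritation. Nurses rate ease of application by leg from 1 to 6, and both legs are photographed at each visit. This stands in part, and it limits the severity: a reader might infer that the trial has no paste-versus-dry data, and that is not so. But the symptom items are Yes/No/N/a, they do not grade severity, and they have no Week 0 value. A realist account also has to tie outcomes to the bandage that produced them, which is a matter of attribution and not of power.

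A reader might extend the point to VEINES-QoL and EQ-5D-5L. The document does not support calling these an error. Both are whole-patient tools by nature, and the protocol nowhere says they will compare bandages. It says only that "VEINES-QoL is a patient reported outcome measure score that focuses on lower limb health" and that EQ-5D-5L is a general measure.

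Two doubts concern the forms. The drawn scales are not reproduced in the text at hand, so a single line is inferred from the instruction and from the contrast with Appendix 3. The dressing-change pain readings could in practice be taken leg by leg, but nothing says so, and a two-week recall question cannot produce them in any case.

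Finally, the Timeline section says "Each leg will be randomised to either" one of the three systems. Read alone, this could put the same type on both legs of some patients. That conflicts with the two sections quoted above, so it does not rescue the scales.

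**Conclusion.** The point holds for the pain VAS and the pruritus VAS. As worded, they yield no paste-versus-dry difference in any of the 40 patients, and no graded symptom score in the plan is recorded by leg. It rests on two assumptions: the paste-on-one-leg, dry-on-the-other allocation is the intended one, and the forms carry one scale each, as their instructions imply.

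It should be fixed, but it is not fatal. No stated hypothesis or sample size depends on these scores, and Appendix 3 supplies coarser by-leg answers. It would also be too strong to expect paired differences at all four visits after a repair: Week 0 is baseline, and Week 1 is contaminated by the recall period. VEINES-QoL and EQ-5D-5L remain measures of patient context, and their results should not be read as evidence for one bandage type over the other.

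**What to change.** In Table 1 and Appendix 2:
- Record the pruritus VAS, and the pain VAS at each of its three dressing-change readings, once for the right leg and once for the left, with the bandage code as in Appendix 3.
- Reconcile the two-week recall wording with the dressing-change readings, since one question cannot serve both.
- Decide whether the Week 1 recall should be shortened so that it covers only the time since allocation. If it is not, treat Weeks 4 and 8 as the visits that carry the paste-dry difference.
- Use the Week 0 scores as the per-leg baseline.

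The cost is about four extra VAS lines per visit and a form revision. Bandage allocation, visits and sample size are unchanged. The change has to precede data collection, or apply from the date of amendment, because by-leg scores cannot be reconstructed afterwards.

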# Pruritus visual analogue scores Pruritus visual analogue scale Instructions:

"Please think about any **leg itching** you may have had over the past **2 weeks** and put a cross along the scale that best describes it."

Not itchy at all

**Extremely itchy** 

#### Quality of life: EQ-5D-5L

Under each heading, please tick the **ONE** box that best describes your health today.

#### MOBILITY

I have no problems in walking about I have slight problems in walking about I have moderate problems in walking about I have severe problems in walking about I am unable to walk about	
SELF-CARE I have no problems washing or dressing myself I have slight problems washing or dressing myself I have moderate problems washing or dressing myself I have severe problems washing or dressing myself I am unable to wash or dress myself	
USUAL ACTIVITIES (e.g. work ,study, housework, family or leisure activities) I have no problems doing my usual activities I have slight problems doing my usual activities I have moderate problems doing my usual activities I have severe problems doing my usual activities I am unable to do my usual activities	
PAIN / DISCOMFORT I have no pain or discomfort I have slight pain or discomfort I have moderate pain or discomfort I have severe pain or discomfort I have extreme pain or discomfort	
ANXIETY / DEPRESSION I am not anxious or depressed I am slightly anxious or depressed I am moderate anxious or depressed I am severely anxious or depressed I am extremely anxious or depressed	

©EuroQoL Group 1990

# **APPENDIX 3. PATIENT AND NURSE'S EXPERIENCE** PATIENT AND NURSE QUESTIONNAIRE – CLINICAL EXPERIENCE

Bandage used: Right Leg S1F/S1R, S2F/S2R or S3F/ S3R (circle what applies)	S1F = UrgoK2 S1R = UrgoK2 Lite S2F = Coban2 S2R = Coban2 Lite S3F = AndoFlex TLC Calamine S3R = AndoFlex TLC Lite Zinc
FOR THE PATIENT TO COMPLETE	
Please rate the following as your overall experience of circle):	of wearing this bandage (please
Has this bandage helped with your pain?	Yes No N/a
Has this bandage improved your comfort?	Yes No N/a
Has this bandage improved your ability to wear normal footwear and clothes?	Yes No N/a
Has this bandage stayed in place?	Yes No N/a
Has this bandage improved your skin condition?	Yes No N/a
Has this bandage improved your skin irritation?	Yes No N/a
Please add any further comment of your personal experience	
FOR THE NURSE TO COMPLETE	
Prior to last bandage application, was the leg washed with Hydromol mixed in warm water?	Yes No N/a
Prior to last bandage application, was the leg debrided using a debridement cloth or tenatome?	Yes No N/a
Looking at the leg, has this bandage helped improve the leg's skin condition?	Yes No N/a
Looking at the leg, has this bandage reduced the leg's skin irritation?	Yes No N/a
Looking at the leg, has this bandage helped with wound healing?	Yes No N/a

Looking at the leg, has this bandage helped with wound

malodour?

Yes

No N/a

	S1F = UrgoK2
	S1R = UrgoK2 Lite
Bandage used: Left Leg	
	S2F = Coban2
S1F/S1R, S2F/S2R or S3F/ S3R (circle what applies)	S2R = Coban2 Lite
	S3F = AndoFlex TLC Calamine
	S3R = AndoFlex TLC Lite Zinc

#### FOR THE PATIENT TO COMPLETE

Please rate the following as your overall experience of wearing this bandage (please circle):

Has this bandage helped with your pain?	Yes	No	N/a	
Has this bandage improved your comfort?	Yes	No	N/a	
Has this bandage improved your ability to wear normal footwear and clothes?	Yes	No	N/a	
Has this bandage stayed in place?	Yes	No	N/a	
Has this bandage improved your skin condition?	Yes	No	N/a	
Has this bandage improved your skin irritation?	Yes	No	N/a	
Please add any further comment of your personal experience				
FOR THE NURSE TO COMPLETE				
Prior to last bandage application, was the leg washed with Hydromol?	Yes	No	N/a	
Prior to last bandage application, was the leg washed with Hydromol? Prior to last bandage application, was the leg debrided using a debridement cloth or tenatome?	Yes Yes	No No	N/a N/a	
Prior to last bandage application, was the leg washed with Hydromol? Prior to last bandage application, was the leg debrided using a debridement cloth or tenatome? Looking at the leg, has this bandage helped improve the leg's skin condition?	Yes Yes Yes	No No No	N/a N/a N/a	
Prior to last bandage application, was the leg washed with Hydromol? Prior to last bandage application, was the leg debrided using a debridement cloth or tenatome? Looking at the leg, has this bandage helped improve the leg's skin condition? Looking at the leg, has this bandage reduced the leg's skin irritation?	Yes Yes Yes Yes	No No No	N/a N/a N/a N/a	
Prior to last bandage application, was the leg washed with Hydromol?Prior to last bandage application, was the leg debrided using a debridement cloth or tenatome?Looking at the leg, has this bandage helped improve the leg's skin condition?Looking at the leg, has this bandage reduced the leg's skin irritation?Looking at the leg, has this bandage helped with wound healing?	Yes Yes Yes Yes	No No No No	N/a N/a N/a N/a	

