# Data analysis

# **Refining Programme Theories**

Excel/word documents will be used to store data. The data collected from the recruited participants will be analysed collectively, using descriptive statistics where appropriate and inductively bringing together the various data sources in emerging themes. This will demonstrate how theories evolve in the course of the study. Engagement, involvement, and collaboration between each member of the research team will take place to refine theories to understand when, for whom and in what circumstances are two different types of compression bandages selected in clinical practice. It is hoped and expected that at the end of the study, new guidance for nursing staff will be developed to guide the selection of compression bandages.

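### The footwear-and-clothes item is scored once per leg but is partly a whole-person question and joins two questions, so a paste-versus-dry difference on it may be diluted

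*Protocol*

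**What the plan says.** Under Compression bandage selection procedure, the protocol states that "one leg will be bandaged in 'paste' compression and one leg in 'dry' compression, through a process of randomisation". The two products are thus worn side by side on the same person. The Safety section notes that this departs from routine practice, where "usually both legs would be compressed using the same product for ease of procurement".

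Appendix 3 (Patient and nurse questionnaire – clinical experience) prints the patient block twice, once for the right leg and once for the left. Each block identifies the leg and the bandage used, and opens with the instruction "Please rate the following as your overall experience of wearing this bandage (please circle". Six Yes/No/N/a items follow. One of them, identical on both forms, is "Has this bandage improved your ability to wear normal footwear and clothes". Each block ends with a free-text line: "Please add any further comment of your personal experience".

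Table 1 (Timeline) schedules this questionnaire at Weeks 1, 4 and 8. The forms do not tell the patient to consider only the shoe or garment on the leg in question, or how to answer when the other leg is the limiting one.

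**The concern.** A split-leg comparison needs outcomes that belong to one leg. Most of the six items meet that need: a bandage slips, or the skin under it improves, on one leg. Wearing normal clothes does not, because a pair of trousers covers both legs. Footwear lies in between: each shoe goes on one foot, but shoes are usually worn as a pair. A patient held back by one bandage may reasonably answer No on both forms. That answer is true of the person but says nothing against the other bandage. With the same product on both legs, as is usual in routine care, the ambiguity would matter little. It matters here because the legs differ.

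The item also puts two questions behind one tick. A patient helped with shoes but not with clothes, or the reverse, cannot record that in the Yes/No answer.

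At stake is the per-leg patient evidence on everyday function. As printed in Appendix 2, VEINES-QoL and EQ-5D-5L are whole-person instruments, and the pain and itch scales do not name a leg. In Appendix 3, this item comes closest to asking about daily function by leg. The study hopes to produce guidance on bandage selection, so a weakened contrast on wearability could be read as little difference between the types.

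**Working it through.** The protocol states no figure to reproduce. Under Patient recruitment it says "40 patients will be recruited for having bilateral leg ulceration", without a significance level, power, effect size or test. The analysis is described as "using descriptive statistics where appropriate and inductively bringing together the various data sources in emerging themes". The calculation below is therefore only an illustration of how the item behaves.

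**Inputs**
- From the protocol: n = 40 patients, two legs each, one paste and one dry.
- Assumed: pA and pB, the proportions who would answer Yes to the item as worded (that is, improved) if each leg could be judged alone; independence of the two legs within a patient; all 40 patients answering Yes or No on both forms.
- Assumed: s, the share of patients who give one common answer for both legs, Yes only if both legs merit Yes. This share is taken to be unrelated to the leg-level answers.

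**Formulae**
- Observed Yes rate, bandage A: (1 − s)·pA + s·pA·pB
- Observed Yes rate, bandage B: (1 − s)·pB + s·pA·pB
- Observed difference: (1 − s)·(pA − pB), because the common term cancels
- Expected patients whose two legs differ: n·(1 − s)·[pA(1 − pB) + (1 − pA)pB]

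**Worked case**, pA = 0.60, pB = 0.40, s = 0.50:
- Joint Yes = 0.60 × 0.40 = 0.24
- A: 0.5 × 0.60 + 0.5 × 0.24 = 0.42
- B: 0.5 × 0.40 + 0.5 × 0.24 = 0.32
- Difference: 0.42 − 0.32 = 0.10, against 0.20 at leg level
- Patients with differing legs: 40 × 0.5 × (0.36 + 0.16) = 10.4, against 40 × 0.52 = 20.8 with no pair-answering

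**Range over s**

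| s | 60% v 40%: difference (points) | differing pairs of 40 | 70% v 30%: difference (points) | differing pairs of 40 |
|---|---|---|---|---|
| 0% | 20 | 20.8 | 40 | 23.2 |
| 25% | 15 | 15.6 | 30 | 17.4 |
| 50% | 10 | 10.4 | 20 | 11.6 |
| 75% | 5 | 5.2 | 10 | 5.8 |
| 100% | 0 | 0 | 0 | 0 |

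The proportional shrinkage does not depend on the rule behind the common answer. Any patient who gives the same answer for both legs adds zero to the paired difference. The double question needs no calculation: one tick cannot carry two answers that disagree.

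**The case against.** The strongest reply is that the form already asks for a leg-specific judgement. Each block names the leg and product, the instruction refers to the bandage on that leg, and the item asks what this bandage has done. A shoe goes on one foot, so Yes on one form and No on the other is a natural pair of answers. This stands in part: it lowers the likely share of pair-answering, more for shoes than for clothes, but it does not tell the patient what to do when the other leg is the obstacle.

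Second, the free-text line lets a patient say which leg or which garment is the problem, and the planned synthesis can use such comments. A patient who manages only one of the two can circle No and explain. So the item is answerable. What is lost is detail, and its recovery depends on patients volunteering it.

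Third, the direction is not certain. A patient wearing two products at once might contrast them and exaggerate the difference. This also stands: dilution follows from pair-answering, and the protocol does not establish which habit will prevail.

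A reader might go further and infer that the bulkier bandage decides the answer for both legs, so that the difference is hidden and the item will be reported as showing no effect. The protocol does not support that. It describes every product as two-layer and gives no thickness, it says nothing on how patients will respond, and it plans no test whose null result would be reported.

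**Conclusion.** The concern holds as a limited measurement weakness. The item mixes a leg-level with a person-level outcome and joins two questions. Answers for one leg may be influenced by the bandage on the other, and any paste-versus-dry difference may then shrink in proportion to the share of patients who answer for the pair. That share is unknown. Complete loss of the difference is the extreme case in which every patient does so.

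The conclusion rests on the split-leg design and the printed wording, both of which are plain in the protocol. The size rests on assumed Yes rates and an assumed share, and should be read as a scale of what could happen. The weight is low: one of six Yes/No/N/a patient items, in a 40-patient descriptive realist evaluation that declares no primary outcome. It is still worth correcting, because the wording is fixed in the protocol's own appendix and answers given for the pair cannot be separated by leg at analysis.

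**What to change.** On both leg forms in Appendix 3, replace the item with two. Keep its present opening, so that both still ask about improvement, and end the first with *your usual shoe on this foot* and the second with *your usual clothing over this leg*. Add one line of instruction above them: *answer for this leg only, whatever the other leg allows*. Keep Yes/No/N/a and the free-text line.

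The cost is one more tick per leg at Weeks 1, 4 and 8, which is two per visit and six per patient over the study, plus a revised form. Treatment, visits and sample size are unaffected. The clothing item may still carry some spillover, because trousers are one garment over both legs, so its per-leg answers should be read with more caution than those for the shoe. If forms have already been completed with the combined item, report those answers separately from answers to the new pair.
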